6.10.2.2.2 Analysis

Change from baseline (Day 1) for the ETDRS on the worst eye at Day 14, Day 28, Day 42 and Day 56 will be analysed using a mixed-effect model for repeated measures. The model will include baseline ETDRS as a covariate, treatment group and visit as fixed factors and the treatment-by-visit interaction.

The variance/covariance matrix structure that results in best model fit will be selected using the process described in section 6.10.2.1.2.

Assumptions of normality will be assessed visually using diagnostic plots. Should assumptions of normality not hold, transformations such as percentage change and ratio to baseline will be considered. If there remains uncertainty regarding the assumptions, a non-parametric analysis may be considered as an alternative.

The LS means and 95% confidence interval will be presented for each visit and treatment. The adjusted LS mean difference (nomacopan - placebo) and 95% confidence interval will be presented for each visit.

A null hypothesis of no change in ETDRS at Day 56 between treatment groups (nomacopan - placebo) will be assessed and a p-value will also be reported.

6.10.2.2.3 Listing

All visual acuity data will be listed, including the worst eye assessment.

6.10.2.3 Clinical scores

Clinical scores will only be available for the eye judged as worst affected at each visit by the patient. In the event that the patient judges both eyes to be equally affected the right eye will be assessed. The eye that the scoring was recorded on will be captured on the eCRF and presented in the listing.

The clinical score is calculated from the Symptom and Sign sub-components.

For AKC and VKC the Symptom sub-component consists of 5 items and the Sign subcomponent consists of 6 items with each item being given a score between 0 and 3. The Total and Symptom and Sign sub-components are calculated as the sum of all items, Symptom items and Sign items respectively giving a possible range of 0 to 33 on the Total score, 0 to 15 on the Symptom score, and 0 to 18 on the Sign score.

For SAC and PAC the Symptom sub-component consists of 4 items and the Sign subcomponent consists of 5 items with each item being given a score between 0 and 3. The Total and Symptom and Sign sub-components are calculated as the sum of all items, Symptom items and Sign items respectively giving a possible range of 0 to 27 on the Total score, 0 to 12 on the Symptom score, and 0 to 15 on the Sign score. The sign sub-component items are different for SAC and PAC to AKC/VKC.

For all indications, should an item be missing there will be no imputation and the score will be missing for that timepoint.

6.10.2.3.1 Descriptive Summaries

Descriptive statistics for the observed and change from baseline (Day 1) clinical scores for the total clinical score, the overall symptom and sign subcomponent scores and each item score will be presented for each treatment group at each visit for the recorded eye.

6.10.2.3.2 Analysis

Change from baseline (Day 1) for the total score at Day 14, Day 28, Day 42 and Day 56 will be analysed using a mixed-effect model for repeated measures. The model will include baseline total clinical score as a covariate, treatment group, visit and patient group (AKC/VKC or SAC/PAC) as fixed factors and the treatment arm by visit interaction.

The variance/covariance matrix structure that results in best model fit will be selected using the process described in section 6.10.2.1.2.

Assumptions of normality will be assessed visually using diagnostic plots. Should assumptions of normality not hold, transformations such as percentage change and ratio to baseline will be considered. If there remains uncertainty regarding the assumptions an alternative analysis, for example non-parametric analysis, may be considered.

The LS means and 95% confidence interval will be presented for each visit and treatment. The adjusted LS mean difference (nomacopan - placebo) and 95% confidence interval will be presented for each visit.

A null hypothesis of no change in clinical score at Day 56 between treatment groups (nomacopan - placebo) will be assessed and a p-value will also be reported based on the relevant mixed-effect model.

Where there is sufficient data (see section 6.2) the item scores will be analysed using the same method as for the total score.

Where there is a sufficient number of patients receiving rescue therapy, additional analysis (as described above) may be conducted using the same methods as the recorded clinical scores by imputing the worst-case score for all post-rescue therapy visits.

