| 10 | . Corneal perforation |
| | . Uncontrolled glaucoma (increase in dose of glaucoma |
| | medication or surgical intervention for glaucoma within 3 |
| | months prior to entry) |
| 12 | . Pregnancy (females) |
| | . Breast feeding (females) |
| | . Known allergy to ticks or severe reaction to arthropod venom |
| | (e.g. bee or wasp venom) |
| 15 | . Use of topical ocular steroids within 7 days of the Screening |
| | visit |
| 16 | . Failure to satisfy the PI of suitability to participate for any |
| | other reason |

| Treatment Regimen: | Part 1: Sterile eye drops 0.25% w/v (2.5 mg/mL), solution in 6mL glass vials containing 1mL solution. Eye dropper pipettes will also be supplied. |
|---------------------------|--|
| | Part 2: Sterile rVA576 0.25% w/v (2.5 mg/mL) or placebo solution in 6 mL glass vials containing 1 mL. Eye dropper pipettes will also be supplied. |
| | The product should be administered as one drop to each eye every 12 hours (i.e. twice daily) for a total of 56 Days. |
| | Background therapy: Patients should continue on whatever topical therapy they are on at the time of screening (ciclosporin or antihistamines) but this should remain stable during the trial. Lubricants and artificial tears may be used ad libitum but should not be administered for 15 minutes before or after the trial medication. In the event of worsening of signs or symptoms that, in the clinician's opinion is so severe as to necessitate a change of medication, ciclosporin and/or antihistamines may be introduced or increased in dose/frequency and this will be considered as a treatment failure for purposes of efficacy analysis. Topical corticosteroids may be added following introduction or increase in ciclosporin/antihistamine therapy if considered necessary. |
| | Should not be on topical ocular steroids at start of the trial but may be used as rescue therapy during the trial if necessary (see above) |
| Duration of Treatment: | 56 Days each for active and placebo dosing plus 7 (± 2) days between screening and entry and 28 (± 2) days between final trial visit and follow up visit. Total trial duration 6-12 months. |

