6.3 Dosing Scheme

Part 1: The product will be supplied as a sterile 0.25% solution in 6 mL glass vials containing 1 mL of rVA576 solution. Single use eye dropper pipettes will also be supplied. The vials are for single use (one drop to each eye) and must be retained and returned to the site at each clinic visit.

Part 2: The product will be supplied as a sterile 0.25% solution in 6 mL glass vials containing 1 mL of solution of either rVA576 or placebo. Eye dropper pipettes will also be supplied. The vials are for single use (one drop to each eye) and must be retained and returned to the site at each clinical visit.

The patients will be randomised to receive either rVA576 active or placebo in double masked fashion. The product should be administered as one drop to each eye every 12 hours (i.e. twice daily) for a total of 56 days.

The product should be stored frozen in the site Pharmacy until the first 7 days' supply is to be given to the patient and then every 7 days thereafter. The product once unfrozen should be kept at 2 - 8 °C for a maximum of 7 days.

All patients entering the trial will have been on maximal topical therapy (meaning the maximal labelled dose or frequency of dosing) for at least three months before entry on the study and will continue on this therapy (background therapy) for the duration of the study.

Background therapy:

Patients should continue on whatever topical therapy they are on at the time of screening but this should remain stable during the trial. Lubricants and artificial tears may be used *ad libitum* but should not be administered for 15 minutes before or after the trial medication. In the event of worsening of signs or symptoms that, in the clinician's opinion is so severe as to necessitate a change of medication, ciclosporin and/or antihistamines may be introduced or increased in dose/frequency and this will be considered as a treatment failure for purposes of efficacy analysis. Topical corticosteroids may be added following introduction or increase in ciclosporin/antihistamine therapy if considered necessary.

See Concomitant Medications for further details of choice of eye lubricants.

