Patients should not have used topical ocular steroids for 7 days prior to entry to the trial but, at the discretion of the investigator, may receive them as rescue medication during the trial. A comparison of the number of patients requiring rescue therapy at any stage of the trial and the number on such therapy at the end of the trial will be an additional exploratory endpoint.

Use of systemic immunosuppressives, antihistamines or corticosteroids during the trial is forbidden. Patients who, in the opinion of the investigator, require such treatment will be withdrawn from the trial. If the reason for giving such treatment is related to their primary pathology (AKC, VKC, or severe allergic conjunctivitis (SAC or PAC)) they will be regarded as treatment failures.

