6.8 Rescue Therapy

Topical ocular steroids will be considered Rescue Therapy.

In the event of worsening of signs or symptoms that, in the clinician's opinion is so severe as to necessitate a change of medication, ciclosporin and/or antihistamines may be introduced or increased in dose/frequency and this will be considered as a treatment failure for purposes of efficacy analysis.

The introduction or increase in dose/frequency of ciclosporin or antihistamines will be considered as Rescue Therapy.

After entry into the trial, subjects will be recommended to not receive Rescue Therapy from the first dose of rVA576 as far as possible unless assessed by PI as needed.

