6.9 Safety and Efficacy Assessments

Safety will be assessed by the Investigator from history and clinical examination. Adverse events (AE) will be recorded in the CRFs and in part 2 of the study, a comparison will be made between the number, type and severity of AEs between the treatment groups.

Comfort will be assessed on the basis of the patient diary cards. A comparison of the total comfort scores between the randomised treatment groups in part 2 of the study, will be made at the conclusion of the trial. For each treatment group a total comfort score of < 10 will be deemed to be comfortable/acceptable, 10 - 19 will be moderately uncomfortable, 20 - 29 will be very uncomfortable and > 30 will be severely/unacceptably uncomfortable.

Composite eye sign and symptom scoring will be carried out by the investigator/blind assessor (depending on the part of the study) at each scheduled clinic visit. Symptoms will be scored by the patient in response to specific questioning by the investigator/blind assessor. Signs will be scored by the investigator/blind assessor as a result of the clinical examination. At each visit the patient will be asked which eye feels to be the worst affected at the time of the visit and that eye will be used for the examination. If both eyes seem to the patient to be equally affected the right eye will always be used. The worst affected eye may change from visit to visit.

For each sign/symptom a numerical score 0 - 3 will be awarded (see table in Section 17.1 (AKC and VKC) and 17.2 (severe allergic conjunctivitis - SAC or PAC). These scores will be summed at the conclusion of the examination and this will be known as the composite score. The minimum possible composite score is 0, the maximum 33 (AKC and VKC) or 27 (severe allergic conjunctivitis (SAC or PAC)). All statistical comparisons, in part 2 of the study, will be done on the basis of the composite score for each patient/visit.

MMP-9 detection using the *Inflammadry*[®] device. This device will give a binary (positive/negative) result which will be recorded in the CRFs at each time point and a comparison of the numbers of positives in each randomised treatment group will be made.

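### The protocol counts ciclosporin/antihistamine rescue as a treatment failure for efficacy, but the composite-score model does not apply this, and the SAP's one failure-type analysis is optional and incompletely defined

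*SAP*

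**What the plan says.** **The failure rule.** The protocol synopsis (Treatment Regimen) says that, for severe worsening, "ciclosporin and/or antihistamines may be introduced or increased in dose/frequency and this will be considered as a treatment failure for purposes of efficacy analysis". Section 6.3 has the same wording, and 6.8 repeats it: "and this will be considered as a treatment failure for purposes of efficacy analysis". Section 6.3 adds that patients withdrawn because they need systemic treatment for the eye disease count too: "they will be regarded as treatment failures". It does not say how they enter the analysis.

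**Steroids.** Protocol 6.8 states: "Topical ocular steroids will be considered Rescue Therapy". Section 6.3 allows them in two ways. They may follow a ciclosporin/antihistamine change ("Topical corticosteroids may be added following introduction or increase in ciclosporin/antihistamine therapy if considered necessary"), or patients, "at the discretion of the investigator, may receive them as rescue medication during the trial". The failure sentence does not name steroids given alone.

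**The efficacy analysis.** Protocol 5.1 defines efficacy as the active-placebo difference in mean composite score. Protocol 6.9 says: "All statistical comparisons, in part 2 of the study, will be done on the basis of the composite score for each patient/visit". Protocol 11.3 and SAP 6.10.2.3.2 specify a repeated-measures model for change from baseline, with no failure term or rule. SAP 6.2 leaves missing data missing.

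**The SAP's failure-type analysis.** The last paragraph of SAP 6.10.2.3.2 reads: "Where there is a sufficient number of patients receiving rescue therapy, additional analysis (as described above) may be conducted". It would impute a worst-case score at every visit after rescue.

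**Rescue counts.** SAP 6.10.3.3 tabulates rescue use. Its two-week percentages are taken out of patients whose comfort score could be calculated.

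**The concern.** The protocol gives rescue a statistical role, not only a clinical one. Protocol 11.1 leaves the full detail of the analyses to the SAP. The SAP then lets a score improved by rescue count as an ordinary observation, and its one analysis that penalises rescue need not be run.

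Two analysts could both comply and still run different failure analyses, or none. With 8 patients per arm, one rescued patient is 12.5% of an arm, so a trigger and an imputed value chosen late could visibly change the efficacy estimate. SAP 6.17, which lists departures from the protocol's planned analysis, does not mention the failure rule.

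**Working it through.** There is no plan figure to reproduce, because the documents give no rescue rate, SD or effect size. The check is textual first, then illustrative.

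**Step 1: what happens to each kind of patient**

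| Event | Protocol status | Main SAP model | Optional SAP analysis |
|---|---|---|---|
| Ciclosporin/antihistamine started or increased for worsening | Rescue and failure | Recorded score used | Covered, if run |
| Steroid added after that change | Already a failure | Recorded score used | Covered, if run |
| Steroid only | Rescue, not named as failure | Recorded score used | May be covered (keyed to all rescue) |
| Withdrawn for systemic therapy of the eye disease | Failure | Later visits missing | Not clearly covered |

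For withdrawals, protocol 7.2 stops further study procedures but asks for an end-of-trial visit that is as complete as possible. A composite score may therefore exist. The SAP does not say whether it is analysed, and SAP 6.4 leaves unscheduled post-baseline assessments out of the tables.

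**Step 2: what the optional analysis leaves open**

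- *Trigger.* No number is given. The preceding sentence, on item scores, refers to SAP 6.2; the rescue sentence does not.
- *Value.* Worst case could be the patient's own worst score or the scale maximum (33 for AKC/VKC, 27 for SAC/PAC). The worst-case wording in SAP 6.2 concerns incomplete dates. For a patient at the entry threshold, the maximum means a change of 33 - 18 = +15 or 27 - 15 = +12.

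**Step 3: one rescued patient, by hand**

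Shift in an 8-patient arm mean = (imputed score - recorded score)/8. Assume an AKC/VKC patient with a recorded post-rescue score of 10 and an own worst of 18:

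- own worst: (18 - 10)/8 = 1.0 point
- scale maximum: (33 - 10)/8 = 2.9 points

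**Step 4: simulation, all inputs assumed**

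- 20,000 runs, 8 per arm, 33-point scale, baseline N(21, 3) kept within 18-33.
- Mean Day 56 change -3 on placebo and -9 on active, reached linearly. SD 5 per visit, AR(1) correlation 0.7 over Days 14, 28, 42 and 56.
- Rescue at Day 28 for the worst-changing patients in each arm, lowering the score by 6.
- Own worst = highest of baseline, Day 14 and Day 28, capped at the scale maximum.
- ANCOVA on baseline as a stand-in for the repeated-measures model.

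| Rescued, placebo vs active | Recorded | Own worst | Scale maximum |
|---|---|---|---|
| 3/8 vs 1/8 | -4.50 | -6.67 | -8.39 |
| 2/8 vs 2/8 | -6.03 | -4.99 | -4.51 |

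Recorded versus own worst:

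- unequal rescue: 6.67 - 4.50 = 2.17 points, towards active
- equal rescue: 6.03 - 4.99 = 1.04 points, towards placebo

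The last cell can be checked by hand. With a quarter of each arm set to the same ceiling, only the other 6/8 carry the assumed 6-point effect, and 6/8 x 6 = 4.5.

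If the full effect is present from Day 14 instead, the rows are -4.49, -6.55, -8.41 and -6.03, -5.30, -4.52. The gap between own worst and maximum for 3/8 vs 1/8 (about 1.7 to 1.9 over the two courses) ran from 0.85 with a baseline mean of 26 to about 2.2 with SD 3 or with rescued patients chosen at random.

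**Step 5: the rescue percentages**

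Suppose 2 of 8 patients are rescued in an interval and neither has a calculable comfort score. The SAP percentage is 2/6 = 33.3% (or 0/6 if the numerator is restricted too), against 2/8 = 25.0%. SAP 6.10.2.1 is also inconsistent on when that score is missing. It sets the total to missing at 20 or more missing points of 140, then says the total is derived whatever is missing.

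**The case against.** The strongest reply is that the protocol never specifies a failure-based composite-score analysis. Sections 5.1, 6.9 and 11.3 all point to the score itself. Rescue use is an exploratory between-arm comparison, 11.3 names it for analysis, SAP 6.10.3.3 makes the counts compulsory, and SAP 6.5 summarises reasons for withdrawal. On this reading, failures enter through those outputs.

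Part of this stands. A reader might infer that the recorded-score model is wrong, or breaches a model the protocol laid down. The documents do not support that: the model answers a legitimate question and matches 5.1. But the counts are descriptive and do not apply the failure label to any efficacy outcome, although the protocol attaches that label to the efficacy analysis. The two sets of sections still need reconciling.

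It is also fair that protocol 11.5 limits the weight given to any single significant result. That guards against chance findings; it does not settle which question is being estimated.

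Two further inferences go too far:

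- *That the five-result rule in SAP 6.2 is the trigger.* It counts available results per arm and time point, not rescued patients, and the rescue sentence does not refer to it.
- *That withdrawn patients can have no further score.* Protocol 7.2 asks for an end-of-trial visit.

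**Conclusion.** The point holds as a gap between the two documents and within the protocol. A stated failure rule has no planned route into the composite-score analysis, and the one analysis that could carry it is optional, with an open trigger, an undefined value and uncertain coverage. The denominator of the two-week rescue percentages is a separate, smaller fault.

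Under the assumed inputs, the choice between recorded scores and own worst moves the Day 56 difference by about 2.2 points with 3/8 vs 1/8 rescued, and by about 1.0 point in the opposite direction with 2/8 vs 2/8. These figures show that the choice can matter in either direction. They do not predict this trial's result, and they vary with baseline level, SD and who is rescued.

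A reader might instead size the problem as the difference in rescue shares times the rescue effect, which would be zero at equal rescue. That compares recorded scores with hypothetical unrescued ones, a quantity neither document asks for. The two analyses in question differ at equal rescue as well.

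The consequence is confined to reading a secondary efficacy endpoint in an unpowered safety trial. The primary safety endpoint is untouched. It should be fixed before unmasking.

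**What to change.** 1. Reconcile the protocol synopsis, 6.3 and 6.8 with protocol 5.1, 6.9 and 11.3 and SAP 6.10.2.3.2 on how failures enter the efficacy analysis, including steroid-only rescue and systemic-therapy withdrawals. The clinical rescue rules need not change.
2. In SAP 6.10.2.3.2, replace the conditional sentence with a planned failure-based sensitivity analysis, run whenever a failure occurs and reported beside the recorded-score model. State before unmasking which one leads.
3. Define the failure value before unmasking, for example the patient's own worst total score from baseline up to rescue, with the scale maximum as an optional sensitivity value. Say how a score from an end-of-trial visit at withdrawal is handled, state any exception to the no-imputation rule in SAP 6.2, and record the decision in SAP 6.17.
4. In SAP 6.10.3.3, use FAS patients still in the study at the start of the interval as the denominator for the two-week rescue percentages.

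The cost is SAP wording, a protocol clarification and one extra model run. Rescue use is already on the Concomitant Medications CRF page. The downside is that the failure-based result depends on the chosen value and may be less precise; showing both models makes that visible.

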6.10.2.3.3 Listing

All clinical score data will be listed.

6.10.2.4 MMP-9 positive levels

The number and percentage of patients with MMP-9 negative (< 40ng/mL) and positive (≥ 40 ng/mL) assessed using the Inflamma Dry device will be presented for each treatment group at each visit for right and left eyes.

All MMP-9 data will be listed.

6.10.2.5 Tear film break up time

Tear film break up time (TBUT) will only be available for one eye. The eye that the test was carried out on will be captured on the eCRF and will be presented in the listing.

6.10.2.5.1 Descriptive Summaries

Descriptive statistics for observed and change from baseline (Day 1) TBUT will be presented for each treatment group at each visit for the recorded eye.

6.10.2.5.2 Analysis

Change from baseline (Day 1) for TBUT (in seconds) at Day 14, Day 28, Day 42 and Day 56 will be analysed using a mixed-effect model for repeated measures for the recorded eye. The model will include baseline TBUT as a covariate, treatment group and visit as fixed factors and the treatment-by-visit interaction.

The variance/covariance matrix structure that results in best model fit will be selected using the process described in section 6.10.2.1.2.

Assumptions of normality will be assessed visually using diagnostic plots. Should assumptions of normality not hold, transformations such as percentage change and ratio to baseline will be considered. If there remains uncertainty regarding the assumptions a non-parametric analysis may be considered as an alternative.

The LS means and 95% confidence interval will be presented for each visit and treatment. The adjusted LS mean difference (nomacopan - placebo) and 95% confidence interval will be presented for each visit.

A null hypothesis of no change in TBUT at Day 56 between treatment groups (nomacopan - placebo) will be assessed and a p-value will also be reported.

